11.4 Competing Risks

11.4.1 Death

Due to the severity of underlying disease it is possible that patients may die from progression of their disease or complications of their treatment prior to completion of treatment with the study drug. It is estimated that fewer than 5% of study patients will die prior to determination of primary and secondary endpoints. In the event that a participant dies prior to completion of the study data will be included up to the time of their death. No further assumptions will be made regarding future bleeding rates in this population

11.4.2 Hospital Discharge

Patients discharged from the hospital within 30 days of activation of the study drug will receive their assigned study drug up until the day of discharge. The day of discharge will be the final day of therapy with the study drug. They will be contacted at 7 days (+/- 3 days) and 30 days (+/- 3 days) post cessation of the study drug. These visits may take place in the outpatient clinic (if coinciding with a regularly scheduled return appointment) or by telephone. During these visits patients will be asked for any bleeding or thrombotic events since study drug cessation.

11.5 Statistical Analysis Planned

All statistical comparisons will be based on a two-sided model using a 0.05 level of significance and two-sided 95% confidence intervals.

Data on the number of patients screened, the number of patients eligible for study inclusion, the number of eligible patients who consent to study inclusion and the number of consented patients activated to the study drug will be organized in CONSORT diagram. Run chart may also be used to demonstrate study momentum over time period of study enrollment in graphical form. Suppression of fibrinolysis will be analyzed by matched pair analysis using a T-test of means.

For secondary endpoints, events of WHO Grade 2 or higher bleeding will be compared through the use of odds ratio or T-test statistic of means. The mean number of platelet transfusions will be analyzed using a T-test statistic of means.

Patients will be followed for all clinical outcomes regardless of adherence to the prescribed regimen for the study drug.

Additional statistical analysis will be considered at the time of trial completion based on the data obtained.

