Tranexamic Acid is a competitive inhibitor of plasminogen activation and inhibits fibrinolysis. It is available in an intravenous formulation and has been used in pediatric patients to prevent or reduce bleeding in the peri-operative setting, pediatric trauma and with menstrual bleeding [9-14]. Prior studies investigating the use of antifibrinolytic agents in patients with hypoproliferative thrombocytopenia have been limited, but results are encouraging as to its effectiveness [15-18]. However, none of these studies have included pediatric patients to date.

The results of this study will allow the investigators to evaluate recruitment success in order to plan for a larger trial to investigate the efficacy of tranexamic acid in this population. It will also provide evidence as to the safety of tranexamic acid when used as an adjunct to platelet transfusion in pediatric patients with hypoproliferative thrombocytopenia, and may provide a signal as to its effectiveness. Lastly laboratory studies will demonstrate whether the dose strategy for TXA effectively suppresses *in vitro* measures of fibrinolysis. If beneficial, this treatment could potentially lead to a decrease in bleeding episodes and platelet transfusions (with an attendant decrease in transfusion related adverse events) as well as potential savings for healthcare-related costs and improved quality of life.

Objectives

The purpose of this study is to evaluate the feasibility and safety of a randomized controlled trial of tranexamic acid for use in the prevention of bleeding complications in pediatric patients with hypoproliferative thrombocytopenia secondary to chemotherapy or blood and marrow transplantation. A secondary objective is to demonstrate that the TXA dosing strategy suppresses in-vitro measures of fibrinolysis.

Study Design

This will be a double blind, randomized, placebo-controlled trial. Eligible subjects will be identified by research staff or primary physicians after being identified as likely to have platelet counts of $\leq 20,000/\mu\text{L}$ for 5 days or longer. Daily assessments of hemostasis and thrombosis will be conducted via chart review, patient interviews and physical exams.

Table of Contents

1. Summary	7
Figure 1: Trial Entry, Randomization, Treatment and Monitoring Flow Diagram	12
2. Background	13
3. Study Aims and Endpoints	14
3.1: Primary Aims and Endpoints	14
3.2: Secondary Aims and Endpoints	14
3.3: Safety Endpoints	15
4. Population	15

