	
 • Known inherited or acquired prothrombotic disorder • Diagnosis of DIC • WHO Grade 2 or greater bleeding within 48 hours prior to enrollment or study drug activation • Receipt of PEG-asparaginase within 7 days prior to enrollment • Receiving tranexamic acid (or other anti-fibrinolytic agent) or any other pro-coagulant agent; Receiving estrogen derivatives or progestins • Receiving therapy with anticoagulation or antiplatelet therapy • Receiving platelet growth factors • History of thromboembolic event within past six months • History of sinusoidal obstruction syndrome • Visible hematuria • Renal dysfunction (as defined in Section 6, Table 2), receiving dialysis or anuria (defined as <10mL/hr urine over 24H) • History of seizures • Known allergy to tranexamic acid • Pregnancy • Receiving outpatient therapy or predicted to have inpatient hospital stay ≤3 days • Patient with platelet count ≥30,000/uL without predicted fall in platelet count
Study type	
Interventional Allocation: randomized, 1:1 Intervention model: parallel assignment Masking: double blind (subject,

Data category	Information
	
caregiver, investigator, outcomes assessor) Primary purpose: Prevention Phase I
 
Study Period: 18 months

Date of first enrollment	TBD
Target sample size	20
Recruitment status	Pre-Recruitment
Primary outcome(s)	
Determine the feasibility of enrolling and conducting an RCT of tranexamic acid in pediatric patients with hypoproliferative thrombocytopenia
 
To define and describe safety of tranexamic acid administered on this schedule
 
To demonstrate appropriate suppression of in vitro fibrinolytic activity by tranexamic acid administered on this schedule

Key secondary outcomes	
To preliminarily define the reduction in WHO grade 2 or higher bleeding events within the confines of a Phase 1 study
 
To assess the reduction in number of platelet transfusions
 
To assess the reduction in number of red blood cell transfusions

Figure 1. Study Schematic

2. Background

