Additionally, this study will incorporate a secondary translational component utilizing assays of fibrinolysis on samples obtained from patients prior to and following antifibrinolytic therapy. As this study will not be adequately powered to detect differences in the occurrence of bleeding events between patients in the treatment group and the placebo group, identification of the successful impairment of fibrinolysis *in vitro* will provide evidence of adequate antifibrinolytic dosing. Additionally, by better characterizing baseline fibrinolytic activity in pediatric patients with malignancies, this may allow us to identify a subset of patients in whom antifibrinolytic therapy may be the most useful.

3. Study Aims and Endpoints

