3.1 Primary Aims and Endpoints

Aim 1: To determine the safety and feasibility of the use of tranexamic acid in pediatric patients receiving chemotherapy or blood and/or marrow transplantation (BMT)

Endpoint: Incidence of adverse events, serious adverse events and death attributed to study drug; Number of patients screened eligible for enrollment and the rate of recruitment during study period

Aim 2: To evaluate the effectiveness of current dose of tranexamic acid for suppressing *in vitro* fibrinolysis

Endpoint: Measures of fibrinolytic activity at baseline (prior to tranexamic acid infusion) and at steady-state

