8.7 Fibrinolysis labs

Blood samples will be collected at two time points during the study period to assess suppression of fibrinolysis with study dose of tranexamic acid. At time point one, blood will be collected prior to first dose of study drug to measure baseline fibrinolytic activity. At time point two, blood will be collected at one time point on Day 4-6 of treatment, at least six hours after last dose of study drug and prior to next dose of study drug, in order to assess the suppression of fibrinolysis when tranexamic acid is present at steady state. Samples should be processed and frozen within 4-8 hours of collection. Samples will be stored at the Children's Hospital of Pittsburgh. They will be batched together and shipped to UNC Chapel Hill where fibrinolysis assays will be completed in such a way as to allow for minimum shipments. A portion of each patient's frozen sample will remain at the Children's Hospital of Pittsburgh for use in later biomarker assays of fibrinolysis (unless only minimum quantity required by UNC Chapel Hill has been drawn, in which case all of the sample will be shipped.) At UNC Chapel Hill samples will be

stored until fibrinolysis assays have been completed and then will be disposed of. Samples at the Children’s Hospital of Pittsburgh will be stored indefinitely and used until exhausted. Study participants can request in writing that that samples no longer be used for research and any samples will be destroyed. Study sample may be used at later point for additional testing of the effects of tranexamic acid.

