11.1.1 Primary Endpoints

- Assessment of feasibility of recruitment by monitoring number of patients screened, number of patients eligible for enrollment and rate of recruitment (both start-up and ongoing) during study period
- Assessment of safety of tranexamic acid in this population by reported adverse events, serious adverse events and death.
- Assessment of the suppression of fibrinolysis by tranexamic acid will consider the difference in fibrinolytic activity in blood samples obtained from participants at the start of the study prior to receipt of the study drug and after achieving steady state.

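### The only planned fibrinolysis analysis is a before/after paired t-test with no comparison against placebo, so it cannot attribute suppression to tranexamic acid or support the dose

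*Combined protocol and SAP*

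**What the plan says.** Section 11.5 gives a single sentence on this endpoint: "Suppression of fibrinolysis will be analyzed by matched pair analysis using a T-test of means". Section 11.1.1 defines the measure as "the difference in fibrinolytic activity in blood samples obtained from participants at the start of the study prior to receipt of the study drug" and again once steady state is reached. Aim 2 in Section 3.1 has the endpoint "Measures of fibrinolytic activity at baseline (prior to tranexamic acid infusion) and at steady-state". None of the three mentions placebo.

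Sections 8.4, 8.5 and 8.7 schedule one sample before the first dose of study drug and one on Day 4-6, with no restriction by arm. The stated purpose of the second sample is "in order to assess the suppression of fibrinolysis when tranexamic acid is present at steady state".

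The Section 1 summary lists the aim among the primary outcomes: "To demonstrate appropriate suppression of in vitro fibrinolytic activity by tranexamic acid administered on this schedule". Section 2 explains that the trial is not powered for bleeding and that impaired fibrinolysis in vitro "will provide evidence of adequate antifibrinolytic dosing". The hypothesis in Section 11.1 likewise rests partly on the study dose suppressing fibrinolysis sufficiently. By contrast, Section 11.1.2 frames Grade 2 or higher bleeding and platelet transfusions as differences between the arms.

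**The concern.** A paired test asks whether the mean change from baseline differs from zero. It does not ask whether TXA caused the change. The first sample is taken at activation, when platelets are at or below 30,000/µL and expected to fall further (Section 5.2). The second comes several days later, in patients who are having chemotherapy or transplantation and may be transfused. Any of these could move a fibrinolysis assay in both arms, and regression to the mean could add to it. A blinded, randomised placebo arm sampled on the same schedule is the means of removing such a common change, and the stated analysis makes no use of it.

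The error can run either way. A common fall would be read as drug suppression, and a common rise would hide real suppression. Since this result is the plan's stated support for the dose ahead of a larger efficacy trial, either mistake would carry forward.

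**Working it through.** **Inputs from the plan.** 10 activated patients per arm (Section 5.3), 20 in total (Section 11.7), 1:1 allocation (Section 11.2), two-sided 0.05 (Section 11.5). The sample size rests on feasibility, so there is no power figure for fibrinolysis to reproduce. The accrual figure is consistent with it: 14 per year × 1.5 years = 21, against a target of 20.

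**Assumptions.** The documents give no assay SD, expected effect or time trend. Effects and drift are therefore in units of the SD of within-patient change, over a range. Where ANCOVA is used, the correlation between baseline and follow-up is assumed to be 0.5 unless stated otherwise.

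**Formulas.**
- Paired t-test on n pairs with mean change d: noncentral t, n − 1 df, noncentrality d√n.
- Two-sample t-test on change scores, n per arm, difference d: noncentral t, 2n − 2 df, noncentrality d√(n/2).
- Pooled paired test with a true drug effect, and ANCOVA: simulation.

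**1. False positives: no drug effect, common drift.** Example at 0.5 SD: noncentrality is 0.5√10 = 1.58 for TXA pairs only (critical value 2.26, 9 df) and 0.5√20 = 2.24 for all pairs pooled (critical value 2.09, 19 df).

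| Common drift (SD) | Paired, 10 TXA | Paired, 20 pooled | Between arms |
|---|---|---|---|
| 0 | 5.0% | 5.0% | 5.0% |
| 0.25 | 10.9% | 18.6% | 5.0% |
| 0.5 | 29.3% | 56.5% | 5.0% |
| 0.75 | 56.2% | 88.9% | 5.0% |
| 1.0 | 80.3% | 98.9% | 5.0% |

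The between-arm column is the change-score test, in which a common drift cancels. ANCOVA also stays at about 5% in simulation.

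**2. Power when the drug works.**

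| Scenario | Paired, 10 TXA | Paired, 20 pooled | ANCOVA |
|---|---|---|---|
| Effect 1.0 SD, no drift | 80% | 47% | 66% |
| Effect 1.5 SD, no drift | 99% | 75% | 94% |
| Effect 1.0 SD, opposing drift 0.5 SD | 29% | 3% | about 65% |

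In the last row the TXA arm changes by −1.0 + 0.5 = −0.5 SD and the placebo arm by +0.5 SD. The pooled mean change is therefore zero and the pooled test has nothing to detect.

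**3. Choice of between-arm method at an effect of 1.0 SD.** The change-score t-test has 56% power. ANCOVA has 72%, 66% and about 60% at correlations 0.3, 0.5 and 0.7.

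**4. Detectable effect at 80% power.** 1.00 SD for the paired test on 10 patients. For the change-score comparison, 1.32 SD with 10 v 10 and 1.51 SD with 8 evaluable per arm.

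**The case against.** The plan does not say that placebo is left out. Section 11.3 says participants are analysed by randomised group, so pooling is the least natural reading, and the most striking figures (56%, 99%, 47%, 3%) belong to that reading. Paired tests run arm by arm would at least display any placebo drift. The drift is assumed: at 0.25 SD the TXA-only error rate is 11%, and at 0.1 SD only 6%. If the true effect were 2 SD, the TXA-only test and ANCOVA would both have about 99% power even against a 0.5 SD opposing drift. The aim's status is also mixed: Sections 1, 3.1 and 11.1.1 treat it as primary, while the synopsis says "A secondary objective is to demonstrate that the TXA dosing strategy suppresses in-vitro measures of fibrinolysis" and Section 2 calls the laboratory component secondary. Finally, the samples exist in both arms, so a between-arm comparison could still be done later.

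Much of this is fair on emphasis, but it does not rescue the test. Section 11.3 defines who is analysed and names no contrast for fibrinolysis. Separate tests in each arm do not estimate a difference between arms. The Section 11.5 provision for further analysis depends on the data and is not pre-specified. A large drug effect would protect power, but not the false-positive rate when the drug does nothing.

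One point stands alongside the concern: no threshold for sufficient suppression is given, so a significant between-arm difference would not by itself show that the dose is adequate.

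**Conclusion.** The concern holds. Whether the pairs are pooled, TXA-only or tested arm by arm, the stated analysis cannot separate a drug effect from a change common to both arms, and the plan leaves that choice open. With no drug effect and a drift of 0.25 to 1.0 SD, the nominal 5% error becomes 11% to 80% in TXA pairs alone and 19% to 99% if pooled. The real size depends on drift and assay variability, which the documents do not give. That the test cannot attribute the change to TXA follows from the design and needs none of those figures. The correction should be made before unblinding, because this is the endpoint on which the dose argument rests.

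**What to change.** In Section 11.5, make the main Aim 2 analysis a TXA versus placebo comparison of the Day 4-6 value by ANCOVA, adjusted for the pre-dose value, reporting the adjusted difference with its 95% confidence interval. Report paired changes separately by arm as description. Align Sections 3.1 and 11.1.1 with this, name the assay measure, state before unblinding what degree of suppression counts as sufficient, and reconcile the primary and secondary labels.

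The between-arm comparison changes wording only: no new samples, visits or patients. Its price is nominal power. If there were no drift, the TXA-only paired test would have 80% against 66% at 1.0 SD, and 99% against 94% at 1.5 SD. That advantage comes from assuming what the placebo arm is there to test. If ANCOVA is not wanted, a between-arm t-test on change scores gives the same protection against common drift, with 56% power at 1.0 SD.

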11.6 Sequential Stopping Rules

When 50% of target sample has been recruited (10 patients) an independent Data and Safety Monitoring board will conduct an interim analysis to monitor study progress, integrity, and patient safety (by review of incidence of adverse events and serious adverse events). The exact stopping rule will be chosen in discussion with the DSMB prior to the interim analysis. There will be no early stopping boundary for efficacy of tranexamic acid over placebo.

11.7 Sample size

The goal of this study is to recruit a total of 20 participants in order to demonstrate study feasibility. Study goal is to recruit patients at a rate of 1- 2 participants per month. Our estimate is that for every two patients eligible for study inclusion and approached for trial enrollment there will be one patient who will sign consent for study enrollment. This study will not be adequately powered to detect a significant reduction in bleeding rates. However, the goal is to establish safety of tranexamic acid and ability to conduct a larger trial of efficacy in the future. Results of this trial, including recruitment rate, will allow for calculations as to the ideal sample size, ideal number of trial sites and the ideal length of study period for future trials.

If accrual to the study does not meet expectation then study inclusion criteria will be reviewed to consider including patients with additional diagnosis and/or platelet transfusion thresholds.

12. Risks Management Procedures

12.1 Protection Against Risks

All research interventions/activities will be conducted in private patient care areas. The collection of sensitive information about subjects is limited to the amount necessary to achieve the aims of the research, so that no unneeded sensitive information is being collected.

All demographic and clinical information about the subject will be stored on a Case Report Form which will be completed for each subject enrolled into the clinical study. The Investigator will review, approve and sign/date each completed CRF; the Investigator's signature serving as attestation of the Investigator's responsibility for ensuring that all clinical and laboratory data entered on the CRF are complete, accurate and authentic.

The data will be stripped of individual identifiers and stored anonymously on CRF with a unique study subject ID. No personal identifier will be used in any publication or communication used to support this research study. The study subject ID code will be

used in the event it becomes necessary to identify data specific to a single subject. Representatives from the IRB and FDA are eligible to review medical and research records related to this study as a part of their responsibility to protect human study subjects in clinical research. All medical and research records will be de-identified prior to being photocopied. Study results will not be given to individual subjects but will be published in the open literature and made available as a matter of public record. Data forms will be held securely in a locked file at the desk of one of the primary investigator at the trial site.

Information linking subject identifiers with the coded subject number will be stored in a password protected document on the UPMC Secure OneDrive network and accessed using the UPMC network. Screening log documenting a list of all patients screened for eligibility will be stored on a password-protected document on the UPMC secure OneDrive network and accessed using the UPMC network. These documents will be destroyed upon completion of study enrollment and data collection. Access to data will be limited to the Investigators and study staff under the supervision of the Investigators.

Blood specimens collected for fibrinolysis labs will be stripped of subject identifiers and labelled according to a similar coding protocol as described above. Blood specimens shipped to UNC research labs for fibrinolysis assays will not contain any identifying information. Remaining specimens will be disposed of following completion of assays. Blood specimens maintained at the Children's Hospital of Pittsburgh of UPMC will be labelled according to a similar coding protocol as described above. They will be stored indefinitely unless requested otherwise in writing with patient and used for later assays of biomarkers of fibrinolysis.

All staff involved in this study are properly credentialed and instructed in the areas of testing, confidentiality, and safety.

The Investigator will retain the data for the entire period of this study and will retain the specified records and reports for up to two years after investigations under the IND have been discontinued and the FDA so notified. The Investigator may continue to use and disclose subjects' de-identified information for the purpose of this study for a minimum of seven years after final reporting or publication of the study. If the subject and/or legal representative decide to withdraw or be withdrawn from study participation, they may request that the study data and samples be destroyed. Subject names or other directly identifiable information will not appear on any reports, publications, or other disclosures of clinical study outcomes.

12.2 Data Monitoring and Interim Analysis

Study monitoring will be the responsibility of the Principal Investigator. The investigator will maintain regular correspondence with study staff and monitor compliance with the investigation plan and relevant regulations and maintenance of complete records.

A Data Monitoring and Safety Board (DMSB) has been established. The DMSB is independent of the study organizers and will consist of three individuals with expertise in

the field of Hematology/Oncology, Bone Marrow Transplantation and Transfusion Medicine. The DSMB will meet after enrollment of the first 10 patients and at the conclusion of the trial to review study progress (including patient recruitment and protocol adherence) as well as safety data (Serious adverse events, adverse events, bleeding events and mortality). More frequent meetings may be requested by the DSMB if necessary for adequate review of safety. During the period of recruitment to the study, interim data will be supplied, in strict confidence, to the DSMB along with any other data the committee may request.

The Adverse Event Reports will be included in the reports. The DSMB will have access to all data. Data will be provided in aggregate with both arms combined and also disaggregated by arms A and B without revealing the identity of the arms. Should DSMB findings require breaking of the study blind, then unblinded data will be provided. In light of these interim analyses the DSMB will advise the study investigators on its view:

- The trial be stopped for reasons of patient safety
- The protocol be better modified to protect patient safety

Unless one of these events were to occur the investigators will remain ignorant of interim results.

A copy of the DSMB findings and recommendation will be submitted to the local IRB.

13. Records and Documentation

